5.4 Inclusion/Exclusion Criteria

Inclusion Criteria:

- 1) Age 18-79 years
- 2) Unilateral transtibial amputation
- 3) Been fit with a prosthesis and used it for at least 6 months
- 4) Wear the prosthesis for 4 or more hours on average per day
- 5) Ambulate without upper extremity aids
- 6) Able to walk for 30 minutes on a treadmill

Exclusion criteria:

- 1) Improper fit and suspension with current prosthesis and one cannot be achieved with clinical resources (determined at initial visit)
- 2) Current skin irritation or injury on residual limb
- 3) Osteoarthritis, injury, or pain that interferes with walking ability
- 4) Currently incarcerated
- 5) Pregnant (determined via self-report)

- 6) Inadequate cognitive function or language proficiency to consent to participate
- 7) High (>20%) coronary heart disease risk at 10 years as determined by their Framingham Risk Score

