Our research prosthetist may begin the fitting process for the two study prostheses during the baseline visit, but this process may take place over 2-3 visits. Once both study prostheses fit well, participants will be randomly assigned to wear either the perforated prosthetic liner system or the novel prosthesis during their usual daily activities for two weeks. During the daily use periods, participants will be instructed to check their limb for redness and/or irritation twice a day and if they notice any issues they should contact us immediately for instructions. We will assist with arranging any necessary follow-up care as needed.

Step Count

During the daily use periods, an electronic step counter, taped to the prosthetic pylon/ankle, will collect step-count data. The step data will be collected from the counter when participants return for the next study visit.

Heart Disease Risk Screening Test

During the baseline or prosthetic fitting study visits, prior to the treadmill walk in the 95°F temperature condition, we will screen participants for cardiac problems. We will use the Framingham Risk Score calculator (<https://www.mdcalc.com/framingham-coronary-heart-disease-risk-score>), an age and sex-specific algorithm that calculates the risk for developing cardiovascular disease at 10 years. Participants who have a high (>20%) coronary heart disease risk at 10 years will be withdrawn from the study. The screening test requires the following information: age, sex, smoker, currently on any medication to treat high blood pressure, systolic blood pressure, total cholesterol, and high-density lipoproteins (HDL) cholesterol. The first four items will be obtained by self-report. Systolic blood pressure will be measured with an existing portable digital blood pressure monitor. Total cholesterol and HDL cholesterol results, from within the last 2 years, may be obtained from VA or UW medical records, another medical facility via a release of records request, participant self-report, or by blood draw at the VAPSHCS clinic. If we determine that a participant's risk of heart problems is too high for this study we will advise them to follow-up with their regular medical care provider, and they will not be able to participate further in the study. If a participant is unable to continue in the study, they will be compensated for their effort.

Visit: Study Prosthesis 1

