After two weeks of using the first study prosthesis, participants will return to the VA for a data collection visit. Participants will be instructed to drink approximately 8 to 15 ounces of water two

hours before their study visit and to bring a pair of shorts and a t-shirt to wear, but we will provide this clothing if they prefer. We will repeat the procedures described above in the Baseline Visit to measure skin health and Socket Comfort Score.

While the prosthesis is off, we will make sure the socket and other key components are dry and we will weigh them. Participants will be provided with fresh/dry socks to wear during the procedures. Participants will be asked to change into the shirt and shorts and put the prosthesis back on. A private area to change will be provided. Participants will be asked to wear a wristwatch-style heart rate monitor during the study visit. We will also place a small absorbent pad on the calf of the intact leg to collect sweat. The pad will be attached to the skin using a sticky waterproof covering to prevent evaporation. We will also draw a mark on the skin of the residual limb at the top edge of the socket liner so we can measure how much the liner slips.

When ready, participants will enter the climate-controlled space set at 35° C (95 °F) and 50% relative humidity. Participants will sit for a 30-minute acclimation period and will then be asked to walk on a treadmill at their pre-determined self-selected walking speed for up to 30 minutes or until they feel like the prosthesis may slip off. The duration of activity will be timed, but we anticipate all participants will be able to walk for 30 minutes. Participants will be allowed to drink water as desired during the trial, and we will record the amount of fluid they drink. Handrails and a chair will be present in case participants feel unsteady or wish to take a break.

For safety purposes, we will track participants' heart rate (via the wristwatch monitor) throughout the test. For participants who do not take a beta-blocker medication (self-report), we will stop the test if their heart rate exceeds 75% of their age-adjusted maximum heart rate (220 minus age in years) for 3 consecutive minutes. For participants who do take a beta-blocker medication, we will stop the test if their heart rate exceeds 110 beats per minute for 3 consecutive minutes.

[figure not shown]

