Participants could get overly hot and tired from walking in the heated room. Although unlikely, this could cause them to faint or to have a cardiac event. Participants will be asked to not consume caffeine, tobacco, and alcohol for two hours prior to each visit. They will also be instructed to drink 8-15 ounces of water prior to each visit involving walking in the hot climate-controlled space.

Participants will also be encouraged to drink water as desired during the testing to stay hydrated. Handrails and a chair will be present. The Framingham Heart Risk screening will exclude individuals with risk factors for a cardiac event. Heart rate (beats per minute) will be tracked throughout the treadmill walks. For participants who do not take a beta-blocker medication (self-report), we will stop the test if their heart rate exceeds 75% of their age-adjusted maximum heart rate (220 minus age in years) for 3 consecutive minutes. For participants who do take a beta-blocker medication, we will stop the test if their heart rate exceeds 110 beats per minute for 3 consecutive minutes.

Participants may feel fatigued during or shortly after the study visits. It is possible that participants may experience some emotional or physical stress while adapting to wearing an unfamiliar prosthesis. Participants will be instructed to inform us if they feel dizziness, pain, or discomfort during the procedures and we will stop the activities to address any reported issues as needed.

Subjects may have razor burn and some embarrassment as their hair grows out from the areas shaved for the skin health tests.

The waterproof covering used to seal the gauze for perspiration collection may cause mild skin discomfort or irritation while worn or when removed (feels similar to removing a band-aid).

It is also possible that participants may experience stress or inconvenience by coming to the VA for multiple visits. Participants are free to withdraw from the study at any time.

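### At ages 74 to 79 the heart-rate stop limit for beta-blocker users is slightly looser than the limit for non-users; a 'whichever is lower' clause would remove the reversal

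*Protocol*

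**What the plan says.** Protocol section 5.5 (Visit: Study Prosthesis 1) sets two heart-rate rules for the treadmill walk in the chamber at 35 °C and 50% relative humidity. The group is decided by self-reported beta-blocker use.

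- **Non-users** are stopped if their "heart rate exceeds 75% of their age-adjusted maximum heart rate (220 minus age in years) for 3 consecutive minutes".
- **Users** have a fixed limit with no age term. For participants "who do take a beta-blocker medication, we will stop the test if their heart rate exceeds 110 beats per minute", again for 3 consecutive minutes.

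Section 5.6 repeats both rules. For users it reads: "we will stop the test if their heart rate exceeds 110 beats per minute for 3 consecutive minutes". The two sections agree with each other. Neither links the two limits, caps one by the other, or explains how 110 was chosen.

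The first inclusion criterion in section 5.4 is "Age 18-79 years". Beta-blocker use is not an exclusion, and the separate rule shows that users are expected.

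Two other safeguards bear on the point. Under the heart disease risk screening in section 5.5, "Participants who have a high (>20%) coronary heart disease risk at 10 years will be withdrawn from the study". Section 5.6 adds: "Participants will be instructed to inform us if they feel dizziness, pain, or discomfort during the procedures", and activities are then stopped as needed.

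**The concern.** One limit depends on age and the other does not, so their order can change within the eligible age range. For most ages the user limit is well below the non-user limit, so the separate rule acts as the more cautious one. If the order reverses at the top of the range, the oldest beta-blocker users may continue at a sustained heart rate that would stop a non-user of the same age.

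Heart rate is the only numerical physiological stop criterion during the walk, and section 5.6 accepts that the heat could lead to fainting or a cardiac event. Each participant does the walk three times, once per prosthesis. What is at stake is the coherence of a safety rule. Nothing shows that any hypothesis, endpoint or analysis would be affected.

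**Working it through.** **Inputs**

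- Eligible ages: 18 to 79 (section 5.4).
- Non-user limit: L(age) = 0.75 × (220 − age) (sections 5.5 and 5.6).
- User limit: 110 bpm at every age (sections 5.5 and 5.6).
- Both must be exceeded for 3 consecutive minutes, so duration does not separate the groups.

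The protocol gives no derivation for 110, so there is no figure of its own to reproduce. The check compares the two limits age by age.

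**Crossing point**

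0.75 × (220 − age) = 110, so age = 220 − 110/0.75 = 73.33 years.

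Below this age the user limit is stricter. At age 50, for example, L = 0.75 × 170 = 127.5 against 110. In completed years the user limit is lower at 18 to 73 (56 ages) and higher at 74 to 79 (6 ages).

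**Size around and above the crossing**

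The whole-beat columns show the first integer reading that exceeds each limit. They assume that the monitor reports whole beats, which the protocol does not state.

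| Age | Non-user limit (bpm) | 110 minus non-user limit | First whole beat over, non-user | First whole beat over, user | Whole-beat gap |
|---|---|---|---|---|---|
| 73 | 110.25 | −0.25 | 111 | 111 | 0 |
| 74 | 109.50 | 0.50 | 110 | 111 | 1 |
| 75 | 108.75 | 1.25 | 109 | 111 | 2 |
| 76 | 108.00 | 2.00 | 109 | 111 | 2 |
| 77 | 107.25 | 2.75 | 108 | 111 | 3 |
| 78 | 106.50 | 3.50 | 107 | 111 | 4 |
| 79 | 105.75 | 4.25 | 106 | 111 | 5 |

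The affected ages are 74 to 79 with or without rounding. As a share of (220 − age), 110 bpm is 110/170 = 64.7% at age 50, 110/146 = 75.3% at 74 and 110/141 = 78.0% at 79.

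In practice, a 79-year-old holding a steady rate between 106 and 110 bpm would be stopped after 3 minutes as a non-user but not as a beta-blocker user.

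**Effect of a cap**

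Take the user limit as min(110, 0.75 × (220 − age)). It equals 110 at every age from 18 to 73, so nothing changes there. At 74 to 79 it equals the non-user limit (109.5 falling to 105.75). No eligible age then has a user limit above the non-user limit.

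**The case against.** The strongest reply is that nothing in the protocol says the two limits must be ranked. They are separate rules for separate groups, and 110 bpm is not presented as derived from the 75% rule. Whether 110 is too high for a beta-blocker user in the late seventies is a clinical question that the documents do not answer. This stands: the finding shows an unexplained change of order, not a wrong figure or a contradiction.

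A second reply concerns scale. An affected person must be 74 to 79, take a beta-blocker, pass the Framingham screen, walk without upper-extremity aids and manage 30 minutes on a treadmill. That person must then sustain a rate inside a band at most 4.25 bpm wide, since anything sustained above 110 stops the test anyway. Enrolment is at most 40. Walking is at self-selected speed, with breaks on request, water, handrails and a chair, and the Medical Monitor can stop the protocol or remove a participant. All of this stands and keeps the point small. It does not supply a reason for the order of the limits: the Framingham screen acts before the walk, and symptom reporting depends on the participant.

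A third reply is that the cap gives older users an equal limit, not an extra margin. That is also true. The cap removes the reversal and claims no more. If users need a lower limit than non-users at these ages, that is for the Medical Monitor to decide.

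Finally, the SAP is dated April 2023 and written in the past tense. If testing is finished, the value lies in any reuse of this heat-walk procedure.

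**Conclusion.** The point holds and is minor. At ages 74 to 79 the stop limit for beta-blocker users is looser than the limit for non-users by 0.5 to 4.25 bpm, with no stated reason and no correcting clause in either section.

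The arithmetic is certain, because it uses only the two stated rules and the stated age range. The whole-beat figures (1 to 5) also assume integer readings. The clinical importance of the gap is not established. The documents do not give the number of beta-blocker users aged 74 to 79, and it may be zero. Sample size, power and alpha are untouched. The case for acting is that a safety rule should be coherent over every age it covers, and that the correction costs almost nothing.

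**What to change.** In both section 5.5 (Visit: Study Prosthesis 1) and section 5.6, set the beta-blocker limit to 110 bpm or 75% of (220 minus age in years), whichever is lower, keeping the 3-minute duration and subject to the Medical Monitor's agreement. Leave the eligible age range and the non-user rule as they are. If 110 was chosen deliberately for the oldest users, a sentence giving the reason would settle the matter instead.

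The cost is one clause in two places. The only downside is that a beta-blocker user aged 74 to 79 may occasionally have a walk stopped slightly earlier.

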5.6 Risks and Risk Management

Please note, the increase in physical risks associated with participation in this study only represent a small increase from those encountered in daily life of the participant population.

It is possible that participants may experience an injury (e.g., arising from a trip or a fall while walking on a treadmill or while wearing a study provided prosthesis during the at-home acclimation periods) and/or discomfort (e.g., mild to moderate muscle soreness, excessive skin dryness, blisters, or other soft tissue irritation while in the lab or during the at-home acclimation period), because of walking with the study-provided prostheses. It is possible that a component failure or malfunction of the prostheses could cause a soft tissue injury (e.g., soreness, bruising, scrape) or other minor mechanical injury (e.g., knee or ankle joint soreness). Care will be taken to properly fit the prostheses. Only trained study staff will place and remove the guaze for trapping moisture to mimimize risk of injury. Participants will only be asked to walk on the treadmill at a speed they are comfortable with. To minimize the risk of study prostheses failure, these devices will be thoroughly tested on a benchtop and a certified prosthetist will also evaluate the quality of the prostheses prior to them being worn by participants. Additionally, most of the prosthetic componentry are commonly used, commercially-available devices. Participants will be instructed to exhibit caution while acclimating to walking with a new or modified prosthesis, and they will be asked to check their skin for redness and/or skin irritation twice a day during the daily use periods. If skin issues arise participants will be instructed to contact study staff. These are the same instructions provided when a patient receives a new or different prosthesis as part of a clinical prescription. Since participants will have a chance to wear each of the study prostheses prior to wearing them home, we do not expect any problems to arise during the two-week at-home portion of the study. Participants will be asked to contact us immediately in the event of any study-related pain or injuries to schedule an examination.

Participants could get overly hot and tired from walking in the heated room. Although unlikely, this could cause them to faint or to have a cardiac event. Participants will be asked to not consume caffeine, tobacco, and alcohol for two hours prior to each visit. They will also be instructed to drink 8-15 ounces of water prior to each visit involving walking in the hot climate-controlled space.

Participants will also be encouraged to drink water as desired during the testing to stay hydrated. Handrails and a chair will be present. The Framingham Heart Risk screening will exclude individuals with risk factors for a cardiac event. Heart rate (beats per minute) will be tracked throughout the treadmill walks. For participants who do not take a beta-blocker medication (self-report), we will stop the test if their heart rate exceeds 75% of their age-adjusted maximum heart rate (220 minus age in years) for 3 consecutive minutes. For participants who do take a beta-blocker medication, we will stop the test if their heart rate exceeds 110 beats per minute for 3 consecutive minutes.

Participants may feel fatigued during or shortly after the study visits. It is possible that participants may experience some emotional or physical stress while adapting to wearing an unfamiliar prosthesis. Participants will be instructed to inform us if they feel dizziness, pain, or discomfort during the procedures and we will stop the activities to address any reported issues as needed.

Subjects may have razor burn and some embarrassment as their hair grows out from the areas shaved for the skin health tests.

The waterproof covering used to seal the gauze for perspiration collection may cause mild skin discomfort or irritation while worn or when removed (feels similar to removing a band-aid).

It is also possible that participants may experience stress or inconvenience by coming to the VA for multiple visits. Participants are free to withdraw from the study at any time.

The PI will ensure the study procedures are being properly followed by keeping the research staff well informed of the current study procedures through regular/ongoing contact. Although an injurious fall or a prosthetic component failure related to this protocol is unlikely, we will tabulate a list of any such reports that occur during the study and compare it with corresponding data available in the literature. This will allow us to analyze how much of an increased risk was due to the administered protocol. After each report of an AE, SAE or an unanticipated problem, we will evaluate study procedures for previously-assessed risks, and will determine whether any changes to the protocol are necessary to minimize risks. The use of any procedures or equipment determined to be problematic will be suspended until these changes have been fully implemented and approved by the IRB.

Privacy and Confidentiality

See section 7.0 below for Information Security, Privacy, and Confidentiality related procedures.

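### The only written cardiac entry rule is a predicted-risk score that takes no cardiac history, so known heart disease with a score of 20% or less does not bar entry to the 35 °C treadmill sessions

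*Protocol*

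**What the plan says.** Protocol section 5.4 has one cardiac criterion, the last of its exclusions: "High (>20%) coronary heart disease risk at 10 years as determined by their Framingham Risk Score".

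Section 5.5 (Heart Disease Risk Screening Test) applies it at the baseline or fitting visits, ahead of the first hot walk. The stated purpose is that "we will screen participants for cardiac problems". The tool is described as "an age and sex-specific algorithm that calculates the risk for developing cardiovascular disease at 10 years". Its inputs are listed: "The screening test requires the following information: age, sex, smoker, currently on any medication to treat high blood pressure, systolic blood pressure", followed by total and HDL cholesterol. The consequence is also stated: "Participants who have a high (>20%) coronary heart disease risk at 10 years will be withdrawn from the study". Cholesterol results up to two years old "may be obtained from VA or UW medical records, another medical facility via a release of records request, participant self-report", or by a blood draw at the clinic. The section closes by saying that a participant whose "risk of heart problems is too high for this study" is referred to their usual provider and goes no further.

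Section 5.6 accepts that overheating could, though this is unlikely, lead to fainting or a cardiac event. Among the safeguards it lists: "The Framingham Heart Risk screening will exclude individuals with risk factors for a cardiac event".

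**The concern.** The step is presented as a screen for cardiac problems, but the tool it uses forecasts new disease from risk factors. It does not ask whether the person already has heart disease. For a heat-and-exercise exposure, existing disease is the more direct question, and the written criteria leave it out.

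What is at stake is participant safety. The target population makes the question relevant. Section 5.4 admits people up to age 79 with any cause of amputation. Section 2 names veteran amputees as the target and cites 3000 to 5000 VA lower limb amputations a year of diabetic or dysvascular origin. Sections 5.5 and 5.6 also provide for participants who take beta-blockers. Against this, the study seeks active prosthesis users, so known heart disease may be uncommon among those who enrol.

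**Working it through.** The plan gives no figure to reproduce. The check sets the eligibility and screening text side by side.

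1. **What the score predicts.** Section 5.5 describes the risk of developing disease over 10 years. It is a forecast, not a check for present disease.

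2. **What the score asks.** The inputs are age, sex, smoking, blood-pressure medication, systolic pressure, total cholesterol and HDL cholesterol, 7 in all. Inputs on cardiac history: 0 of 7.

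3. **What section 5.4 asks.** There are 6 inclusion and 7 exclusion criteria: 6 + 7 = 13. Criteria naming existing heart disease: 0 of 13. Exclusion 7 is predicted risk. Exclusion 3 covers osteoarthritis, injury or pain that hinders walking. It is not limited to orthopaedic pain, so angina that limits walking might fall under it. A past infarction, heart failure or an arrhythmia without such pain would not. Inclusion 6 requires the ability to walk for 30 minutes on a treadmill, which is a test of function and does not ask about history.

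4. **Whether another threshold exists.** The closing statement in section 5.5 about risk being too high gives no cut-off of its own. The only one in that section is the score above 20%, the same as in section 5.4.

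5. **Result for one case.** Take a person with a prior infarction, no pain on walking, and a score of 20% or less. Exclusion 7 does not apply, exclusion 3 does not apply, and no other criterion concerns the heart. The person is eligible on the written criteria.

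6. **Exposure.** Each session in section 5.5 is 30 minutes seated plus up to 30 minutes walking at 35 °C and 50% relative humidity: 30 + 30 = up to 60 minutes. There is one session for each of the three prosthetic systems, so 3 × 60 = up to 180 minutes in total.

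7. **The sentence in section 5.6.** Smoking and treated high blood pressure are inputs to the score, not exclusions. A smoker, or a person treated for high blood pressure, who scores 20% or less stays in. The sentence therefore describes a wider screen than the rule provides.

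**The case against.** Several points on the other side have force.

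- **Section 5.6 is not a second rule.** A reader might infer that it conflicts with sections 5.4 and 5.5. It does not. It names the same screen, the threshold is identical in the two operative sections, and nobody would enrol from a risk narrative. It is a loose summary that needs a wording edit.
- **Some material is unseen.** Section 5.2 refers to an attached Screening Script, which may ask about cardiac history. Section 5.5 links to an online calculator whose conditions of use are not in the documents. A reader might infer that people with known heart disease were in fact walked in the chamber. The documents do not show that. The point concerns the written criteria only.
- **Other safeguards exist.** They include clinician agreement or referral on some recruitment routes, self-selected speed, heart-rate limits (with a separate limit for beta-blocker users), stopping for symptoms, discretionary withdrawal (section 5.8) and a Medical Monitor with authority to stop (section 6). These reduce the risk. None of them is an entry rule on cardiac history. The heart-rate and symptom stops act once the exposure has begun, the discretionary powers state no cardiac criterion, and referring providers are briefed on the same criteria that omit heart disease.
- **How much to screen is a clinical and ethics-board judgement.** That is so, and it is why clearance by a study clinician is offered as an alternative to outright exclusion. It does not explain why the question goes unasked in the written criteria.

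**Conclusion.** The point holds as a gap in the written entry criteria. The one cardiac rule rests on a score that, as the protocol describes it, cannot detect existing heart disease, and nothing else in section 5.4 does so, apart from the possible catch of walking-limiting angina under exclusion 3. Because the protocol itself names a cardiac event as a hazard of the hot room, this is more than missing detail.

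Its size in terms of harm is unknown. The documents do not show how many candidates with known heart disease would score 20% or less, and the number may be small. The conclusion assumes that section 5.4 is the full list of operative criteria. If the Screening Script already holds a rule on cardiac history, the gap reduces to one of documentation.

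The sample size, power and analysis model are not touched.

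**What to change.** At the heart-risk step in section 5.5, before the score is calculated, ask about known cardiovascular disease (for example prior infarction, angina, heart failure or significant arrhythmia), using self-report or the medical record. A positive answer either excludes the person or requires documented clearance by a study clinician before the first heat session. List this in section 5.4. If the Screening Script already covers it, state its rule there.

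As a minor edit, reword section 5.6 to say that the screen removes people with a predicted 10-year risk above 20%.

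The cost is one or two questions at a visit that already takes place, answered from sources that step already uses, plus a little clinician time for each clearance. A few candidates may be lost; the documents do not allow an estimate.

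The SAP, dated 10Apr2023, is written in the past tense, so testing may be finished. In that case, describe the screen accurately in reports and carry the criterion into later heat-chamber protocols.
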